#### **Hypnosis-guided echo infiltration technique - Experimental arm:**

Hypnosis will be started after the result of the randomisation, the patient will be taken care of by the nurse trained in hypnosis (see § 4.4 description of the method used).

When the patient is ready, just after the hypnosis session, the nurse will disinfect the patient's hand in 3 steps with an iodinated skin antiseptic and the rheumatologist will perform the infiltration in a standardised way.

In both groups, the Spielberger Anxiety-Trait Scale (STAI form Y-B) will be collected before the intervention and before hypnosis (experimental arm). This score will be used to characterise and describe patients' anxiety before the intervention.

In both groups, the Spielberger Anxiety-Status Scale (STAI form Y-A) will be performed 5 minutes after the infiltration procedure.

The pain VAS will be collected before the hypnosis intervention in order to characterise the pain related to the pathology.

[figure not shown]
The pain VAS will then be collected 5 minutes after the infiltration procedure in order to characterise the pain linked to the infiltration procedure.

The use of analgesic treatments by the patient before the ultrasound guided infiltration will be collected.

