## **1. RATIONALE FOR THE STUDY**

### ***1.1. POSITIONING OF THE RESEARCH***

Echo guided hand infiltration is usually prescribed to relieve chronic pain. According to *the International Association for the Study Pain*, pain is "an unpleasant sensory and emotional experience associated with actual or potential tissue damage, or described in terms suggestive of such damage [1]".

Echo guided infiltration is a relatively common procedure and is generally considered to be locally painful. This pain induced by the treatment, leads to a strong apprehension among patients who have to undergo this procedure.

In order to reduce the stress of the patients, several approaches were put in place, namely: explanation of the procedure, setting up a relaxed atmosphere (notably through discussion). All these elements constitute a form of hypnosis known as conversational. Nevertheless, according to our observations, it remains insufficient for the management of the pain of infiltration.

The practice of hypnosis to improve patient comfort during care has gradually appeared in hospital departments. It is used in surgery, particularly for dressings for burn victims, and increasingly in medicine [2]. Jean-Marc Benhaim, in 2003, indicated that "therapeutic hypnosis is a relational experience bringing into play physiological and psychological mechanisms allowing the individual to better live, to attenuate or to eliminate an acute or chronic painful pathology [3]. The hypnotic state would allow to modulate feelings, in particular emotions such as pain or anxiety [4 & 5].

There are several forms of hypnosis, Ericksonian hypnosis lets the subject solve his problem without direct intervention dictating the solution. It is only necessary to guide him, to choose the ideas, the images... that he likes and that suit him.

This decreases attention, the relationship to reality, spontaneous mental activity and the perception of time, but allows the refocusing of attention towards bodily sensations and mental contents proposed by the induction, as well as concentration and adherence to the imagery.

Erickson said: "go and find your own ways to change".

Ericksonian hypnosis is essentially therapeutic, it is not spectacular. This method can be integrated into the treatment process without significantly increasing the time of the procedure.

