## TIMETABLE OF THE STUDY

Actions	J0 (Inclusion visit)	5 minutes after the action
Patient information	X	
Informed oral consent	X	
Randomisation	X	
Background	X	
Clinical examination	X	
Hypnosis	X	
Medical procedures: ultrasound-guided infiltration	X	
VAS for pathology-related pain	X	
EVA pain of the gesture		X
Anxiety-Trait Scale	X	
Anxiety-Status Scale		X
Analgesic treatments	X	

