#### **4.5. DESCRIPTION OF THE EVALUATION AND THE DATA COLLECTED**

- The Visual Analogue Scale (VAS) of pain is used to assess the progression of pain (Scott & Huskisson, 1976). It is rated from 0 to 10 on a ruler, and the patient must move the cursor on the side without graduation. The nurse records the intensity of the pain felt on the graduated side.
- The Spielberger Anxiety-State Scale is a way of finding out what the patient is feeling "right now, just at this moment". It consists of 20 items (10 items reversed). The scale assesses the intensity of what the patient is feeling. Each item is rated from 1 to 4, with 1 indicating the lowest degree of anxiety and 4 the highest. It is a questionnaire that takes an average of 5-10 minutes to complete. The sensitivity of the items to changes in anxiety in different anxiety-provoking situations has been demonstrated [6].
- The Spielberger Anxiety-Trait Scale captures what the patient "usually" feels. It consists of 20 items (9 items reversed). The scale assesses the frequency of what the patient feels. Each item is rated from 1 to 4, with 1 indicating the lowest degree of anxiety and 4 the highest. This questionnaire takes an average of 5 to 10 minutes to complete.

Both questionnaires have been validated in French [6].

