## 9. Appendix

### *Echelle d'Anxiété-Trait de Spielberger*

## Questionnaire d'anxiété générale de Spielberger

#### Instruction :

Ci-après figurent un certain nombre de déclarations que les gens utilisent souvent pour se décrire. Lisez chacun des énoncés et cochez dans la case appropriée de droite ce qui convient le mieux à la façon dont vous vous sentez en général. Il n'existe ni bonnes ni mauvaises réponses. Ne passez pas trop de temps sur chacun des points, mais donnez la réponse qui semble décrire le mieux ce que vous ressentez généralement. Répondez à toutes les questions et ne cochez qu'une case pour chacune d'entre elles.

	Activités	Etat			
1.	Je me sens dans de bonnes dispositions	 Presque jamais	 Parfois	 Souvent	 Presque toujours
2.	Je me sens nerveux et agité	 Presque jamais	 Parfois	 Souvent	 Presque toujours
3.	Je suis content de moi	 Presque jamais	 Parfois	 Souvent	 Presque toujours
4.	Je voudrais être aussi heureux que les autres semblent l'être	 Presque jamais	 Parfois	 Souvent	 Presque toujours
5.	Je me sens un raté	 Presque jamais	 Parfois	 Souvent	 Presque toujours
6.	Je me sens paisible	 Presque jamais	 Parfois	 Souvent	 Presque toujours
7.	Je suis calme, détendu et de sang froid	 Presque jamais	 Parfois	 Souvent	 Presque toujours
8.	J'ai l'impression que les difficultés se multiplient à un point tel que je ne peux les surmonter	 Presque jamais	 Parfois	 Souvent	 Presque toujours
9.	Je m'inquiète trop à propos de choses qui n'en valent pas la peine	 Presque jamais	 Parfois	 Souvent	 Presque toujours

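### The trait scale is used to describe anxiety before the procedure; state anxiety is measured only afterwards, so the anxiety endpoint has no same-scale baseline

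*Combined protocol and SAP*

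**What the plan says.** Section 4.2 (experimental-arm subsection, in a paragraph covering both groups) schedules STAI Y-B before the intervention, and before hypnosis where it applies. It gives the purpose as follows: "This score will be used to characterise and describe patients' anxiety before the intervention".

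Section 4.5 describes the two forms. Of Y-B it says: "The Spielberger Anxiety-Trait Scale captures what the patient 'usually' feels", and "The scale assesses the frequency of what the patient feels". Of Y-A it says the form captures what the patient feels at that moment, rated by intensity. The trait questionnaire in the Appendix agrees with this, instructing the patient: "donnez la réponse qui semble décrire le mieux ce que vous ressentez généralement".

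Y-A appears at one time point only, 5 minutes after infiltration. Sections 2.2.2, 4.2 and 4.6 say so, and in the study timetable the row "Anxiety-Status Scale" is marked only in the post-procedure column. Section 6.2.1 compares mean post-procedure Y-A between arms by Student's t test, with no covariate.

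Section 1.1 says that the pain of the procedure "leads to a strong apprehension among patients who have to undergo this procedure".

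**The concern.** A trait form completed just before a procedure still reports the patient's habitual level. It does not report how anxious the patient is at that moment. By the protocol's own definitions, the score assigned to anxiety before the intervention is thus the wrong one of the two, and the right one is not collected at that time. Readers of a baseline table built from section 4.2 could take a trait score for pre-procedure apprehension.

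For the anxiety endpoint, the trial could not show whether the arms began with similar state anxiety, could not describe how state anxiety changed over the visit, and would forgo the precision that a same-scale baseline usually gives. Pain is handled differently: section 4.2 takes the VAS both before hypnosis and 5 minutes after the infiltration.

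**Working it through.** **1. Is any state measure taken before the procedure?**

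| Place | Before the procedure | 5 minutes after |
|---|---|---|
| Section 2.2.2 | none | Y-A |
| Section 4.2 | Y-B | Y-A |
| Timetable | trait scale | state scale |
| Section 4.6 | a scale whose name appears mistranslated, at the trait scale's time point | state scale |

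None is scheduled. The state form in the Appendix does ask how the respondent feels now, before a competition. That looks like wording carried over from another setting, and no schedule places the form before the infiltration.

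**2. The plan's own figure.** Section 6.2.2 sizes the trial on pain: difference 2, SD 3, alpha 5% (two-sided assumed), power 80%. The standardised difference is 2/3. The two-sample t-test calculation gives 36.3, so 37 per arm and 74 in total, as stated. The normal approximation gives 36 per arm, 72 in total. Adding 5% gives 74 × 1.05 = 77.7, so 78, against the stated 80. No size is stated for the anxiety endpoint, and nothing below changes 74 or 80.

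**3. Chance imbalance that could not be seen.** With 80 patients allocated 1:1 (section 6.2.8), there are 40 per arm. In SD units of baseline Y-A:

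- standard error of the difference in baseline means = √(2/40) = 0.224
- 95% range = ±1.96 × 0.224 = ±0.44 SD

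Only the share r of such a difference carries over to the post-procedure score, where r is the baseline-to-post correlation. For an assumed r of 0.4 to 0.7 that is 0.4 × 0.44 = 0.18 SD to 0.7 × 0.44 = 0.31 SD. This variation is already part of the standard error of the unadjusted t test.

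**4. Precision available from a baseline Y-A.** Under ANCOVA with a linear baseline term, the residual variance is (1 − r²) times the unadjusted variance. At 40 per arm, 80% power and two-sided 5%, the unadjusted minimum detectable difference is 0.634 SD. With adjustment it is about 0.634 × √(1 − r²).

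| Assumed r | Residual variance | Reduction | Detectable difference |
|---|---|---|---|
| 0.4 | 0.84 | 16% | 0.634 × 0.917 = 0.581 SD |
| 0.5 | 0.75 | 25% | 0.549 SD |
| 0.7 | 0.51 | 49% | 0.453 SD |

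The price is one error degree of freedom: 80 − 2 = 78 becomes 80 − 3 = 77.

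These gains are relative to no adjustment. Y-B is already collected and could itself be a covariate. If it correlates with post-procedure Y-A, part of the gain is available without a new measurement. The documents give no correlation from which to estimate that part.

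**The case against.** The strongest defence is that the plan answers the question it asks. The secondary objective in section 2.2.1 is anxiety 5 minutes after the procedure, with no claim of change from baseline, and the endpoint matches it. A t test on a post-randomisation score needs no baseline to be valid. This stands. A reader might infer that a difference in Y-A could not be attributed to hypnosis because the arms may have started unequal. The documents do not support that: allocation is randomised 1:1, and the confidence interval already allows for chance imbalance in every prior variable, measured or not.

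A second defence is that the wording in section 4.2 may be loose rather than wrong. The preceding sentence names the form correctly, and the reference to before the intervention may mean only the time of collection. That is a possible reading, and it cannot be said that the report will mislabel the score. But the sentence also reads naturally as a claim about pre-procedure anxiety, so clarification is warranted. Rewording would not supply the missing state measure.

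Third, section 1.1 mentions apprehension, but its conclusion concerns pain, which is the primary aim. This limits the weight of the point to a secondary endpoint.

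Fourth, a baseline Y-A gains no precision unless the analysis uses it, and section 6.2.1 adjusts neither outcome. This stands too, so the fix has to name the model.

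**Conclusion.** The point holds as an inexpensive improvement to a secondary endpoint and a correction of one description. Section 4.2 assigns a measure of usual anxiety to describing anxiety before the intervention, and no state measure is taken until after the procedure. The post-procedure comparison is valid and unbiased. The losses are precision, a check of baseline balance in state anxiety, and any description of change.

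The size of the precision loss rests on an assumption. For r between 0.4 and 0.7, the residual variance would fall by 16% to 49% relative to no adjustment, and by less relative to adjusting for Y-B if Y-B is correlated with the outcome. It is tempting to restate this as the trial forgoing 80/0.84 = 95 to 80/0.51 = 157 patients' worth of information. The documents do not support that as a finding: they give no r, and the comparison ignores Y-B. The primary endpoint, its analysis and the sample size are unaffected.

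**What to change.** 1. In section 4.2, the timetable and section 4.6, add STAI Y-A at D0 in both arms, after consent and before randomisation. The trial is open-label, so this order keeps knowledge of the arm from influencing the baseline answers.
2. In section 6.2.1, replace the t test on post-procedure Y-A with ANCOVA: post-procedure Y-A on arm and baseline Y-A, reporting the adjusted difference with its 95% confidence interval. Report baseline Y-A by arm as anxiety before the intervention.
3. In section 4.2, describe Y-B as usual (trait) anxiety.
4. In the Appendix, replace the state form's reference to a competition with wording that fits each time point. The form needs this correction even if it is used only after the procedure.

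The cost is one more self-completed 20-item form, 5 to 10 minutes by section 4.5, within the 2-hour participation in section 3.4. Section 1.2.2.2 calls the questionnaire burden minimal, but that judgement covered the current forms and should be reconfirmed. The same form would be completed twice within the visit, identically in both arms. It needs no new instrument and no extra staff.

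If the sponsor prefers not to add the form, it should still make changes 3 and 4, state that pre-procedure state anxiety is not measured, and consider adjusting post-procedure Y-A for Y-B.

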## TIMETABLE OF THE STUDY

Actions	J0 (Inclusion visit)	5 minutes after the action
Patient information	X	
Informed oral consent	X	
Randomisation	X	
Background	X	
Clinical examination	X	
Hypnosis	X	
Medical procedures: ultrasound-guided infiltration	X	
VAS for pathology-related pain	X	
EVA pain of the gesture		X
Anxiety-Trait Scale	X	
Anxiety-Status Scale		X
Analgesic treatments	X	

#### 4.3. SCHEME OF THE STUDY

#### 4.4. DESCRIPTION AND JUSTIFICATION OF THE METHOD STUDIED

The duration of the hypnosis session will be measured.

The hypnosis session consists of building a "magic glove" with the patient on the hand on which the infiltration will be performed.

The nurse sets up the patient and the rheumatologist uses the ultrasound machine to locate the hand.

The nurse, trained in hypnosis, starts the timer, takes the patient's hand in her hand and begins the hypnosis session. The principle is to get the patient to imagine a glove that they will create to put on their painful hand.

The nurse lets the patient choose the colour, material and asks how far the glove fits on the arm.

The nurse guides the patient to put the glove on each finger by touching the hand.

By suggestion, the nurse forms an anaesthetic area on the hand according to the patient's choice.

If the "protection" is not sufficient, the nurse adds a "strip" or "resin" to increase the anaesthetic.

A phenomenon of catalepsy or levitation of the hand is generated in the patient.

The "magic glove" technique is suitable for hand infiltration because a glove can be slipped onto a hand.

When the patient is ready, the nurse stops the timer and disinfects the patient's hand in 3 steps and the rheumatologist carries out the infiltration in a standardised manner.

#### **4.5. DESCRIPTION OF THE EVALUATION AND THE DATA COLLECTED**

- The Visual Analogue Scale (VAS) of pain is used to assess the progression of pain (Scott & Huskisson, 1976). It is rated from 0 to 10 on a ruler, and the patient must move the cursor on the side without graduation. The nurse records the intensity of the pain felt on the graduated side.
- The Spielberger Anxiety-State Scale is a way of finding out what the patient is feeling "right now, just at this moment". It consists of 20 items (10 items reversed). The scale assesses the intensity of what the patient is feeling. Each item is rated from 1 to 4, with 1 indicating the lowest degree of anxiety and 4 the highest. It is a questionnaire that takes an average of 5-10 minutes to complete. The sensitivity of the items to changes in anxiety in different anxiety-provoking situations has been demonstrated [6].
- The Spielberger Anxiety-Trait Scale captures what the patient "usually" feels. It consists of 20 items (9 items reversed). The scale assesses the frequency of what the patient feels. Each item is rated from 1 to 4, with 1 indicating the lowest degree of anxiety and 4 the highest. This questionnaire takes an average of 5 to 10 minutes to complete.

Both questionnaires have been validated in French [6].

#### **4.6. IDENTIFICATION OF ALL SOURCE DATA NOT IN THE MEDICAL RECORD**

- EVA pain before the infiltration procedure and before hypnosis
- VAS pain 5 minutes after the infiltration procedure
- Anxiety-Treatment scale before the infiltration procedure and before hypnosis
- Anxiety-Status scale 5 minutes after the infiltration procedure

#### **4.7. RULES FOR STOPPING A PERSON'S PARTICIPATION**

##### **4.7.1. Criteria for premature termination of a person's participation in research**

A person's participation may be terminated prematurely for the following reasons:

- Withdrawal of consent by the patient

Subjects will be able to withdraw their consent and ask to leave the study at any time and for any reason.

#### **4.7.2. Data collection schedule**

In case of withdrawal of consent by the patient, and without prejudice to the patient's right, the data already collected will be analysed unless the patient objects.

No other examinations specifically foreseen by the protocol will be carried out and no data will be used according to the patient's wishes after withdrawal of consent.

The discharge of a patient from the study will not change the usual management of the patient's condition.

#### **4.7.3. Discontinuation of part or all of the research by decision of the sponsor (excluding biostatistical considerations)**

Part or all of the study may be stopped permanently or temporarily by decision of the ANSM, the CPP or the Study Sponsor.

In all cases :

- A written confirmation will be sent to the coordinating investigator of the study (specifying the reasons for premature termination).
- All patients in the study will be informed.

### **5. SAFETY ASSESSMENT**

In the context of this Minimal Risk and Minimal Constraint Interventional Research (RIPH Category 2), the adverse event(s) (serious or not) do not have to be notified to the sponsor. Notification must be made within the framework of the vigilance set up in the context of care for the product or practice which is the subject of the research (pharmacovigilance for a drug, materiovigilance for a medical device, etc.) according to the regulations in force.

Only "new facts" and malfunctions that may interfere with the research must be transmitted to the sponsor without delay after becoming aware of them so that corrective measures can be put in place. For these malfunctions, the investigator can use the reporting form to the regulated system, made anonymous (patient inclusion number only).

*A new fact is any new data that may lead to a reassessment of the benefit/risk ratio of the research or the product under investigation, to changes in the use of the product, in the conduct of the research, or in the documentation of the research, or to the suspension or discontinuation or modification of the research protocol or similar research.*

The promoter shall inform the competent authority and the Committee for the Protection of Individuals without delay of the new facts and, where appropriate, of the measures taken, as from the day on which he becomes aware of them.

## **6. DATA MANAGEMENT AND STATISTICS**

### ***6.1. COLLECTION AND PROCESSING OF STUDY DATA***

#### **6.1.1. Data collection**

One case report form (CRF/ eCRF) will be created per patient. All information required by the protocol should be provided in the CRF/eCRF. It should include the data needed to confirm compliance with the protocol and all data needed for statistical analysis; it should identify major deviations from the protocol.

The person(s) responsible for filling in the CRFs/eCRFs (investigator, CRA...) should be defined and is/are identified in the Centre's Delegation of Duties Form (kept in the investigator's folder).

#### **6.1.2. Data coding**

By signing the protocol, the principal investigator and all co-investigators agree to keep confidential the identity of the patients who participated in the study.

The transmission of a person's data for research purposes will therefore only be possible if a coding system is applied; the presentation of the research results must exclude any direct or indirect identification.

The identification of patients will be done according to the order of inclusion of patients by a number automatically assigned by the Clinsight software (eCRF) then completed by the initials of the patients (1st letter of the first name + 1st letter of the last name).

This code will be the only information that will appear on the eCRF notebook and will allow the eCRF to be linked to the patient afterwards.

The investigator is also required to code the patient data on any documents he/she may have in his/her possession (reports of imaging or biological examinations, etc.) which are attached to the eCRF.

A mapping table will be set up in the participating centre. This table will be kept in a secure place by the principal investigator of the centre and will contain the patient code and his or her personal data in order to be able to go back to the patient file in case of missing or erroneous data. No clinical data will be collected in these correspondence tables.

#### **6.1.3. Data processing**

The collection of clinical data will be based on the implementation of a database and the creation of data entry masks similar to the observation book in accordance with the protocol and regulations currently in force.

## 6.2. STATISTICS

### Software

The analyses will be carried out using R software version 3.5.1

